#### 2. Enrollment:

The subjects will be enrolled following the design of a prospective study. The inclusion criteria will be strictly in accordance with the diagnostic criteria of simple steatosis and NASH, as stipulated in the *Chinese Guidelines for the Diagnosis and Treatment of Nonalcoholic Fatty Liver Disease (Revised version 2010)*. The subjects should have a diagnosis of simple steatosis or NASH (age distribution: 18 to 75 years old), with serum alanine transaminase (ALT)  $\leq 2$  times the upper limit of normal, with no other chronic liver diseases or serious complications in other organs, with no malignant tumors.

2.1. Diagnostic Criteria of NAFLD (2010): NAFLD can be diagnosed if the following items 1–4, plus item 5 or item 6 are present:

- i. No alcoholic history (alcohol consumption  $< 140$  g/week for male; or  $< 70$

g/week for female);

- ii. No other diseases that can lead to fatty liver, such as viral hepatitis, drug-induced liver disease, total parenteral nutrition, hepatolenticular degeneration diseases, or autoimmune liver diseases;
- iii. Overweight and/or visceral obesity, hyperglycemia, dyslipidemia, hypertension and other metabolic syndrome;  
Serum transaminase and GGT levels are normal or elevated to a mild to moderate degree;
- iv. Liver imaging findings show diffuse hepatic steatosis;
- v. A liver biopsy meets the histologic diagnostic criteria of fatty liver diseases;

2.2. Diagnostic criteria of simple steatosis: Simple steatosis can be diagnosed if the following item 1-2, plus item 3 or item 4 are present.

- i. Presence of item 1-3 of the clinical diagnosis criteria of NAFLD;
- ii. Liver biochemical tests are normal (blood biochemical analysis);
- iii. Liver imaging findings meet the diagnostic criteria for hepatic steatosis (Fibro touch test);
- iv. A liver biopsy meets the histologic diagnostic criteria for simple hepatic steatosis.

2.3. The diagnostic criteria of NASH: NASH can be diagnosed with the following items 1 to 3 or item 4.

- i. Presence of items 1–3 of the clinical diagnosis criteria of NAFLD;
- ii. Serum ALT levels are persistently elevated for more than 4 weeks;
- iii. Liver imaging findings show diffuse hepatic steatosis;
- iv. A liver biopsy meets the histologic diagnostic criteria for NASH.

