4.4. To evaluate the therapeutic effects of Compound Zhenzhu Tiaozhi capsules on NAFLD

1) To assess whether the content of intrahepatic fat will decrease after 1 month, 3 months, and 6 months of Compound Zhenzhu Tiaozhi capsule therapy.

i. Compare the therapeutic effects of Compound Zhenzhu Tiaozhi capsules at 1 month, 3 months, and 6 months with the baseline (pre-vs.post-therapeutic effects of Compound Zhenzhu Tiaozhi capsules).

ii. Compare the therapeutic effects in the Compound Zhenzhu Tiaozhi capsule group with that of the other three groups at parallel time points (Compound Zhenzhu Tiaozhi capsules vs. Conventional drugs).

2) To assess whether NAFLD-FS will be alleviated after 1 month, 3 months, and 6 months of Compound Zhenzhu Tiaozhi capsule therapy.

i. Compare the therapeutic effects of Compound Zhenzhu Tiaozhi capsules at 1 month, 3 months, and 6 months with the baseline (pre- vs. post-therapeutic effects of Compound Zhenzhu Tiaozhi capsules).

ii. Compare the therapeutic effects in the Compound Zhenzhu Tiaozhi capsule group with those of the other three groups at parallel time points

(Compound Zhenzhu Tiaozhi capsules vs. Conventional drugs).

3) To assess whether insulin resistance will be improved after 1 month, 3 months, 6 months of Compound Zhenzhu Tiaozhi capsule therapy.

- i. Compare the therapeutic effects of Compound Zhenzhu Tiaozhi capsules at 1 month, 3 months, and 6 months with the baseline (pre- vs. post-therapeutic effects of Compound Zhenzhu Tiaozhi capsules).
- ii. Compare the therapeutic effects in the Compound Zhenzhu Tiaozhi capsule group with those of the other three groups at parallel time points (Compound Zhenzhu Tiaozhi capsules vs. Conventional drugs).

4) To assess whether the lipids profile in peripheral blood and liver biochemical parameters (ALT, AST, GGT) will be reduced after 1 month, 3 months, and 6 months of Compound Zhenzhu Tiaozhi capsule therapy.

- i. Compare the therapeutic effects of Compound Zhenzhu Tiaozhi capsules at 1 month, 3 months, and 6 months with the baseline (pre- vs. post-therapeutic effects of Compound Zhenzhu Tiaozhi capsules).
- ii. Compare the therapeutic effects in the Compound Zhenzhu Tiaozhi capsule group with those of the other three groups at parallel time points (Compound Zhenzhu Tiaozhi capsules vs. Conventional drugs).

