2.3 Secondary Objectives

1. To evaluate the change in intestinal mucosal barrier function by detecting biochemical parameters of the intestinal mucosal barrier; to analyze the relationship between NAFLD and the function of the intestinal mucosal barrier.
2. To explore the trends of small intestinal bacterial overgrowth (SIBO) during the treatment process.
3. To investigate whether lipid profiles and liver biochemical parameters are improved following treatment with Compound Zhenzhu Tiaozhi capsules.
4. To assess whether insulin resistance is improved following treatment with Compound Zhenzhu Tiaozhi capsules.
5. To monitor adverse events and put forward specific solutions for the adverse events.

3. Design, evaluation, and plans

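### The ALT, AST and GGT comparison mixes patients enrolled with normal enzymes and patients enrolled with raised ALT, with no split by diagnosis and no adjustment for baseline level (minor)

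*Protocol*

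**What the plan says.** **Who is enrolled.** Protocol section 2 (Enrollment): "The subjects should have a diagnosis of simple steatosis or NASH". ALT may be at most 2 "times the upper limit of normal".

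**Simple steatosis (Protocol 2.2).** "Simple steatosis can be diagnosed if the following item 1-2, plus item 3 or item 4 are present". Item 2 reads "Liver biochemical tests are normal (blood biochemical analysis". It is mandatory on both routes, including the biopsy route.

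**NASH (Protocol 2.3).** "NASH can be diagnosed with the following items 1 to 3 or item 4". Item 2 is "Serum ALT levels are persistently elevated for more than 4 weeks", and item 4 is biopsy. Without biopsy, ALT must therefore be raised, but nothing in item 2 concerns AST or GGT. With biopsy, no enzyme need be raised.

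**The enzyme question.** Protocol 4.4 item 4: "To assess whether the lipids profile in peripheral blood and liver biochemical parameters (ALT, AST, GGT) will be reduced after 1 month", then at 3 and 6 months. The capsule group is compared with its own baseline and with the other three groups at the same time points. SAP 2.3 item 3: "To investigate whether lipid profiles and liver biochemical parameters are improved following treatment with Compound Zhenzhu Tiaozhi capsules". Neither names a diagnosis group, a baseline enzyme subset or an adjustment.

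**Elsewhere.** Allocation is 1:1:1:1 by order of enrolment, with no stratification stated (Protocol 3.2, SAP 3.2). SAP 4.4 lists baseline liver biochemistry as a candidate predictor of therapeutic efficiency, and does not list diagnosis. ALT, AST and GGT are absent from the primary and secondary endpoints (Protocol 4.1 and 4.2 under Endpoints; SAP 4.1 and 4.2).

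**The concern.** The entry definitions divide the sample by the same kind of measurement that is later tested. Patients with simple steatosis start with normal enzymes, and NASH patients diagnosed without biopsy start with raised ALT. This has three consequences.

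- The gap between diagnoses adds to the spread of enzyme values within each arm. That spread is known at entry and can be removed.
- If the drug effect differs between the two groups, the pooled difference is a weighted average of two effects, and the weights are the case mix. Diagnosis is not named among the baseline items in SAP 9.5, so a reader may be unable to interpret the pooled figure.
- A fall from a normal starting value is a reduction, but it does not show that anything abnormal improved. Protocol 4.4 and SAP 2.3 use these two different words for the same question.

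The protocol also expects the capsules to beat simvastatin and metformin on liver biochemical markers (section 5, Expected results, item 3), so the enzyme result is likely to be cited.

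**Working it through.** **The plan's figures.** No enzyme effect, SD or diagnosis mix is given, so there is no enzyme calculation to reproduce. The only usable figure is 44 evaluable patients per group, which was set for the primary endpoint (44/0.9 = 48.9, rounded to 49; 49 x 4 = 196). Everything below is illustration on stated assumptions.

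**Step 1: dilution.** Let s be the share with normal enzymes at entry, Δ the log-scale effect in patients with raised values, and f the fraction of that effect in normal-enzyme patients.

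- Pooled difference = Δ[(1 − s) + s·f].
- Pooled variance = 0.30² + s(1 − s)[Δ(1 − f)]²/2. The second term arises because effects differ within the treated arm only, averaged over the two arms.
- Assumed: Δ = −ln(0.80) = 0.223 (a 20% fall), residual log-SD 0.30, 44 per arm, two-sided 0.05, two-sample t test. The restricted test has 44(1 − s) per arm.

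Example with s = 0.5 and f = 0: difference 0.223 x 0.5 = 0.112; variance 0.09 + 0.25 x 0.0498/2 = 0.0962; SD 0.310; standard error 0.310 x √(2/44) = 0.066; ratio 1.69; power 0.39. The restricted test has 22 per arm: standard error 0.30 x √(2/22) = 0.090; ratio 2.47; power 0.67.

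| s | Pooled fall, f = 0 | Pooled power, f = 0 | Pooled power, f = 1/4 | Pooled power, f = 1/2 | Restricted power |
|---|---|---|---|---|---|
| 30% | 14.5% | 0.65 | 0.75 | 0.83 | 0.82 |
| 50% | 10.6% | 0.39 | 0.56 | 0.73 | 0.67 |
| 70% | 6.5% | 0.17 | 0.36 | 0.60 | 0.45 |

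With no effect in normal-enzyme patients, the restricted test is clearly better. With a quarter of the effect it gains 7 to 11 points. With half the effect it loses 1, 6 and 15 points.

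A second set of assumptions (standardised effect 0.6 in raised patients, s = 50%) gives the same pattern against a restricted power of 0.51. With equal SDs, pooled power is 0.29 at f = 0 and 0.56 at f = 1/2. If the SD in normal-enzyme patients is half as large, it is 0.43 at f = 0 and 0.60 at f = 1/4.

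**Step 2: spread between diagnoses.** Assume s = 0.5, a log gap of 0.4 between the diagnoses, f = 1/4, and a comparison of values at one time point.

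- Difference = 0.223 x 0.625 = 0.139.
- Unstratified: variance 0.09 + 0.25 x 0.4² = 0.13; SD 0.361; standard error 0.077; ratio 1.81; power 0.43.
- Stratified: SD 0.30; standard error 0.064; ratio 2.18; power 0.58.

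These two lines ignore the narrowing of the gap by treatment. Allowing for it, the treated gap is 0.4 − 0.223 x 0.75 = 0.233. The unstratified variance averages (0.13 + 0.1035)/2 = 0.117, and power is 0.47. The stratified variance is 0.09 + 0.167²/16 = 0.0918, and power is 0.57. The gain remains, at about 10 to 15 points here.

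**Step 3: which split.** By Protocol 2.3, biopsy-diagnosed NASH may have normal enzymes, and AST and GGT need not be raised in any NASH patient. Diagnosis is therefore a reasonable stratum, but it does not identify the patients who have something to improve. Each enzyme's own baseline value does.

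**The case against.** The strongest defence has four parts.

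- **Pooling is inferred.** The SAP text available ends with baseline characteristics (9.5) and gives no test or analysis set for the enzymes. The design figure in SAP 3.1 was not available. This stands: pooling is read from the whole-group comparison in Protocol 4.4, and the more basic gap is that no enzyme analysis is specified. That is also why the fix is a matter of wording.
- **The all-patient average is a legitimate target.** It is, and randomisation protects it. A reader might infer that the comparison is biased or invalid; nothing in the documents supports that.
- **Normal values can still fall.** They can. A reader might infer that simple steatosis patients contribute no effect, so that the test should be confined to NASH. The documents give no evidence of a zero effect, and Step 1 shows that restriction can cost power.
- **SAP 4.4 already includes baseline liver biochemistry.** It does, but as a candidate predictor of therapeutic efficiency, carried into the multivariable model only if significant alone. It is not an adjustment of the enzyme comparison.

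The stakes are also low: liver fat is the primary endpoint, and the enzymes are not a listed endpoint. It would be speculation to say that a null enzyme result would be read as no liver benefit.

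**Conclusion.** The concern holds in a limited form. The documents combine patients whose enzymes are normal by definition with patients whose ALT is raised by definition. They then compare whole groups on ALT, AST and GGT with no stated split or baseline adjustment. The result is lost precision and a pooled figure that depends on case mix, not bias between arms.

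The size cannot be derived, because the diagnosis mix, the enzyme SDs and the effects are not given. The gain from 0.43 to 0.58 rests on an assumed even mix, a 0.4 log gap and a quarter effect in simple steatosis. It would be smaller if change from baseline were analysed, since most of the gap would then cancel; the plan does not say which is meant.

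It is tempting to conclude that the elevated-only or NASH-only comparison should be the test of improvement. The figures do not support that: it is better under some assumptions and worse under others. Severity is minor.

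**What to change.** Add to the SAP, before the data are analysed:

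1. For each of ALT, AST and GGT, the main comparison is between arms in all patients, on the log scale, adjusted for that enzyme's baseline value and stratified by simple steatosis or NASH.
2. As a pre-specified supportive analysis, report the between-arm effect in patients above normal for that enzyme at baseline. Define the subset by the enzyme and not by the NASH diagnosis. Keep it between arms, because values selected for being high tend to fall on re-measurement in every arm.
3. Report the simple steatosis/NASH mix in each arm.
4. Do not make the restricted analysis the sole or main test.

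The time points also need reconciling: SAP section 5 has liver biochemistry at admission and 6 months, while Protocol 4.4 uses 1, 3 and 6 months.

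The cost is a few sentences. Diagnosis is established at enrolment, and the enzymes are measured at admission (Protocol, Prescriptions 4.2; SAP 9.5). No patient is dropped from the main comparison. The price is a few model terms and three differently composed supportive subsets, each smaller than the full arms and to be read as estimates with intervals.

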Research and Clinical Pharmacology, 2012, 23 (2): 140-143). Additionally, Compound Zhenzhu Tiaozhi capsules can reduce serum TG, TC, and low-density lipoprotein cholesterol (LDL-C) and increase serum HDL-C levels in a hyperlipidemic rat model (Cited from: Tang Chunping, Gong Mengjuan, Guo Jiao, Yang Chaoyan, Chen Fangchao, Yao Hongxia, Chen Yuefeng. The effects of Fufang Zhenzhu Tiaozhi capsules on blood lipid level and hemorheology of rats with hyperlipemia [J]. Journal of Guangdong Pharmacy College, 2010, 26 (6): 612-616).

Based on the above studies, the investigators hypothesize that Compound Zhenzhu Tiaozhi capsules have the potential to effectively improve NAFLD and related biomedical markers. The possible mechanisms include the improvement of SIBO and the function of the intestinal mucosal barrier. The investigators thus designed the following clinical study to test this hypothesis.

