## **III. Content of the study**

1. To evaluate the relationship between the function of intestinal mucosal barrier, SIBO, and NAFLD;
2. To assess the effects of Compound Zhenzhu Tiaozhi capsules on intrahepatic fat content, hepatic noninvasive score, liver biochemical parameters, blood lipid, and insulin resistance. To evaluate the therapeutic effects of Compound Zhenzhu Tiaozhi capsules on the treatment of NAFLD, and determine whether the risk stratification of atherosclerotic cardiovascular disease (ASCVD) and quality of life (using the 36-Item Short Form Health Survey [SF-36]) can be improved in NAFLD patients with Compound Zhenzhu Tiaozhi capsules.
3. To compare the therapeutic effects of Compound Zhenzhu Tiaozhi capsules with conventional medications in the treatment of NAFLD, and to compare their efficacies in improving the risk stratification of ASCVD and quality of life, as

assessed by the SF-36.

4. Finally, to analyze the relationship of Compound Zhenzhu Tiaozi capsules in improving NAFLD and parameters related to the function of the intestinal mucosal barrier and SIBO.

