### 3. Assignment and intervention:

#### 3.1. Calculation of the sample size and the method of assignment:

Sample size calculation: A total of 196 patients will be enrolled in this study. The sample size is estimated as follows:

Previous studies have reported that the efficiency rate of metformin and simvastatin in the treatment of NAFLD is 36-52%. The investigators hypothesize that the efficiency rate of Compound Zhenshu Tiaozhi capsules will increase by 25% compared to standard drugs.

Statistical calculation:  $P_1 = 69\%$ ,  $P_2 = P_3 = 44\%$ ,  $P_4 = 10\%$ ,  $\delta = P_1 - P_2 = 25\%$ , with  $\alpha = 0.05$ , power = 0.80, and a bilateral test, of which  $w = \sqrt{\frac{\sum_{i=1}^m (P_{t,i} - P_{c,i})^2}{P_{c,i}}}$ , thus n will be equal to 44. Assuming that the rate of loss to follow up is 10%, each group will require 49 cases. Therefore, a total of 196 cases will be required for the four groups.

3.2 The method of assignment: [name], a staff member working in the Department of Statistics in Guangdong Pharmaceutical University, is responsible for generating random sequences using the SAS software. A total of 196 numbers from 1 to 196 will be randomly generated (Supplement 2). Newly diagnosed patients who meet the inclusion criteria will have a case number according to their order of enrollment (for example: case number of the first patient: 001, second patient: 002). They will then obtain the corresponding therapeutic regimens based on their case number with 1:1:1:1 ratio randomized tables. The first group is the TLC group; the second group is the TLC + metformin group (0.5 g, PO tid); the third group is the TLC + Compound Zhenzhu Tiaozhi capsules group (2.52 (four tablets), PO tid); the fourth group is the TLC + simvastatin group (20 mg, PO qn).

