4.5 In the Compound Zhenzhu Tiaozhi capsules group, firstly calculate the changes in the related parameters of NALFD and the changes in the function of intestine microbiota, then evaluate whether the two changes are related to each other.

1) Analyze the relationship between the changes in DAO, D-lac, LPS, intestinal barrier dysfunction grade I, II, III, IV and the reduction in intrahepatic fat at 1 month, 3 months, and 6 months of Compound Zhenzhu Tiaozhi capsule therapy (possible results: unrelated, positively related, or negatively related).

2) Analyze the relationship between the change in SIBO and the reduction in intrahepatic fat at 1 month, 3 months, and 6 months of Compound Zhenzhu Tiaozhi

capsule therapy (possible results: unrelated, positively related, or negatively related).

3) Analyze the relationship between the changes in DAO, D-lac, LPS, intestinal mucosal barrier dysfunction I, II, III, IV and the improvement of insulin resistance at 1 month, 3 months, and 6 months of Compound Zhenzhu Tiaozhi capsule therapy (possible results: unrelated, positively related, or negatively related).

4) Analyze the relationship between the change in SIBO and the improvement of insulin resistance at 1 month, 3 months, and 6 months of Compound Zhenzhu Tiaozhi capsule therapy (possible results: unrelated, positively related, or negatively related).

5) Analyze the relationship between changes in DAO, D-lac, LPS, intestinal mucosal barrier dysfunction I, II, III, IV and the changes in the lipids profile in peripheral blood and liver biochemical parameters (ALT, AST, GGT) at 1 month, 3 months, and 6 months of Compound Zhenzhu Tiaozhi capsule therapy (possible results: unrelated, positively related, or negatively related).

6) Analyze the relationship between the change in SIBO and the changes in the lipids profile in peripheral blood and liver biochemical parameters (ALT, AST, GGT) at 1 month, 3 months, and 6 months of Compound Zhenzhu Tiaozhi capsule therapy (possible results: unrelated, positively related, or negatively related).

7) Analyze the relationship between changes in DAO, D-lac, LPS, intestinal mucosal barrier dysfunction I, II, III, IV and the change in NAFLD-FS at 1 month, 3 months, and 6 months of Compound Zhenzhu Tiaozhi capsule therapy (possible results: unrelated, positively related, or negatively related).

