#### 4. Prescriptions:

4.1: Medications: the dose of Compound Zhenzhu Tiaozhi capsules is 2.52 (4 tablets) tid; metformin is 0.5, tid, and simvastatin is 20mgqn. In general, subjects will be in the hospital for approximately 1 week and continue to receive treatment after discharge from the hospital. The total period of treatment will be 6 months.

4.2: Biochemical assessments: Patients will undergo all the following tests upon admission:

Routine blood test, tumor biomarker tests (alpha-fetoprotein [AFP], carcinoembryonic antigen [CEA], carbohydrate antigen 125 [CA125], and carbohydrate antigen 19-9 [CA19]), uric acid, liver function (representing hepatocyte injury: alanine aminotransferase, aspartate aminotransferase, leucyl aminopeptidase, glutamyl transpeptidase; representing liver secretory function: total bilirubin (TBS), direct bilirubin (DBIL), indirect bilirubin (IBIL); representing liver reserve function: total protein (TP), albumin (ALB), globulin (GLB), and the albumin to globulin ratio (A/G), serum lipid profile (triglyceride, very low density lipoprotein, total cholesterol, low density lipoprotein, high density lipoprotein), FINS (fasting insulin), fasting blood glucose, serum biomarkers of HBV ([i]Hepatitis B surface antigen [HBsAg]; [ii]Hepatitis B surface antibody [anti-HBs]; [iii]hepatitis B e antigen [HBeAg]; [iv]Hepatitis B e antigen antibody [anti-HBe]; [v]Hepatitis B core antibody [anti-HBc]), TP-Ab, syphilis serological test (TRUST), human immunodeficiency virus (HIV), hepatitis C virus antibody,

glycosylated hemoglobin, intestinal mucosal barrier function, coagulation test (prothrombin time [PT], activated partial thromboplastin time [APTT], thrombin time [TT], and fibrinogen [FIB]), Fibrotouch, hydrogen and methane breath test.

4.3 Medical advice on discharge: Physicians need to inform patients regarding the severity of complications in the late stage of NALFD and the importance of early treatment. All the patients should continue treatment after discharge and follow-up in the clinic. They will be required to come back to hospital one month later for re-assessment of the above mentioned items. The appointment telephone number is [name]. The contact doctor is [name].

4.4 All patients will be treated with TLC.

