2.2 Primary Objectives

1. To explore the safety and efficacy of Compound Zhenzhu Tiaozhi capsules for the treatment of NAFLD, compared with metformin and simvastatin.
2. To summarize the regularity of disease progression in the development of NAFLD.
3. To promote the therapeutic options of NAFLD and to improve long-term efficacy.
4. To explore the potential mechanism of Compound Zhenzhu Tiaozhi capsules for the treatment of NAFLD.

[figure not shown]

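### Correlating gut and liver changes within the capsule arm alone can show association, but cannot attribute a gut mechanism to the capsule when every patient also receives TLC.

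*Protocol*

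**What the plan says.** The mechanistic idea appears in three places. The Protocol background offers this hypothesis: "The possible mechanisms include the improvement of SIBO and the function of the intestinal mucosal barrier". Protocol III, item 4, aims "to analyze the relationship of Compound Zhenzhu Tiaozi capsules in improving NAFLD and parameters related to the function" of the mucosal barrier and SIBO. SAP 2.2 lists among its primary objectives: "To explore the potential mechanism of Compound Zhenzhu Tiaozhi capsules for the treatment of NAFLD".

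The analysis meant to serve this is Protocol 4.5. It begins "In the Compound Zhenzhu Tiaozhi capsules group, firstly calculate the changes in the related parameters of NALFD", adds the corresponding intestinal changes, and says to "then evaluate whether the two changes are related to each other". Eight analyses follow, each at 1, 3 and 6 months and all under capsule therapy.

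On treatment, Protocol 3.2 states that "the third group is the TLC + Compound Zhenzhu Tiaozhi capsules group" and that "The first group is the TLC group". Section 4.4 under Prescriptions adds: "All patients will be treated with TLC". So a randomised TLC-only arm exists, but 4.5 does not use it.

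**The concern.** A correlation between two changes within one arm has no contrast in it. Prescriptions 4.4.2 says that diet and activity can lower weight by more than a tenth in overweight and obese people. If weight loss from TLC improves both the gut markers and the liver measures, patients who respond well to TLC will improve on both and those who respond poorly on neither. The two changes then correlate whether or not the capsule acts on the gut.

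What is at stake is the interpretation of the mechanism aim. A positive result under 4.5 would be consistent with the hypothesised capsule pathway and equally consistent with no such pathway. The TLC-only arm, which could help tell these apart, is left out.

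**Working it through.** The plan gives no sample size, effect size or power for the mechanism analysis, so there is no figure to reproduce. The check has four parts.

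**1. Does another planned analysis supply the missing contrast?**
- Protocol 4.3 relates marker levels to liver and metabolic measures in NAFLD patients generally. It uses neither changes nor arms.
- Protocol 4.4 (under Endpoints) compares the capsule arm with the other three on liver fat, NAFLD-FS, insulin resistance, lipids and liver enzymes. It lists no gut marker.
- SAP 2.3 follows barrier change and SIBO trends and names no between-arm comparison.
- SAP 4.4 keeps barrier function and SIBO in the multivariate model of efficacy and is not limited to one arm. Its listed factors include dose of medication, but no randomised-arm term, arm-by-marker interaction or mediation step.

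So whether the capsule shifts a gut marker relative to TLC is not a named comparison anywhere.

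**2. How easily could TLC alone produce the 4.5 result?**
Inputs: n = 44 evaluable per arm (Protocol 3.1), two-sided 5% level. The TLC-driven correlation ρ between gut change and liver change is assumed, because the documents give none.

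In 20,000 simulated trials a shared TLC response drove both changes. The capsule had a direct liver effect and none through the gut. Tests used Fisher's z.

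| Assumed ρ | Capsule-only test significant | Same test in TLC-only arm | Capsule vs TLC difference in correlation |
|---|---|---|---|
| 0.3 | 52% | 51% | 5% |
| 0.4 | 78% | 78% | 5% |
| 0.5 | 94% | 94% | 5% |
| 0.6 | 99% | 99% | 5% |

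Hand check at ρ = 0.3: atanh(0.3) × √41 = 0.310 × 6.40 = 1.98, so the chance of exceeding 1.96 is about 51%.

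**3. What can 44 per arm detect (80% power)?**
- Correlation within one arm: tanh(2.80/√(44 − 3)) = 0.41.
- Association pooled over four arms, n = 4 × 44 = 176: tanh(2.80/√173) = 0.21.
- Capsule vs TLC difference in mean marker change: 2.80 × √(2/44) = 0.60 SD.
- Capsule vs TLC difference between two correlations, power = Φ(|atanh r₁ − atanh r₂|/√(2/41) − 1.96): 70% for 0.5 vs 0, 35% for 0.5 vs 0.2, 41% for 0.6 vs 0.3.

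**4. How many tests does 4.5 imply?**
- Gut markers: DAO, D-lac, LPS, barrier grade, SIBO = 5.
- Outcomes: liver fat, insulin resistance, NAFLD-FS, ALT, AST, GGT = 6, plus lipids. Protocol 4.2 (Secondary endpoints) gives six lipids; Prescriptions 4.2 gives five.
- Tests over three visits: 5 × 12 × 3 = 180, or 5 × 11 × 3 = 165.
- If every null hypothesis were true, 5% of these is 9, or about 8. No multiplicity control is stated.

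**The case against.** The strongest reply is that 4.5 asks only whether two changes are related, and that it answers. Aim III.4 also speaks of a relationship, and the SAP speaks of exploring a potential mechanism. This stands in part. A reader might infer that the analysis fails at its own question, or that the sponsor will report any positive correlation as proof of mechanism. The documents support neither: the written question is one of association, and nothing says how a result will be reported. What remains is the gap between that association and the capsule mechanism named in the background and the SAP.

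A reader might also infer that a mechanism should be claimed only if the marker-outcome association differs between the capsule and TLC arms. That is wrong. If the capsule improves the barrier, and the barrier affects liver fat equally in everyone, the slope is the same in both arms and the interaction is zero. With an assumed marker shift of 0.8 to 1.0 SD, the shift would be detected in 96% to 99.6% of trials, yet the rule would accept the true mechanism in only about 5%, the interaction test's false-positive rate.

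Nor should adjustment for BMI change be the main analysis. It is measured after randomisation, the background reports weight reduction on the capsule in rats, and BMI is a term in the NAFLD-FS formula (SAP section 5).

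Lastly, it is tempting to say that the data already exist in all arms. Prescriptions 4.3 states repeat testing for all patients at one month. The only explicit 3- and 6-month times for gut markers are in 4.5, for the capsule arm. The test lists at the end of the Prescriptions section and in SAP 3.1 omit these markers. Their place among the trial-wide secondary endpoints implies collection in every arm but does not state visits.

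**Conclusion.** The concern holds in this form: 4.5 can describe association within the TLC + capsule arm, but it cannot attribute that association to the capsule, and no other planned analysis names a between-arm contrast on a gut marker.

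The 52% to 99% range shows how readily a shared TLC response could give a significant result. It rests on assumed correlations of 0.3 to 0.6 and 44 evaluable patients, and does not predict this trial. The 0.21 detectable with all four arms applies to a pooled association, which is not by itself evidence of a capsule mechanism. The tests for a difference between arms in correlation have only 35% to 70% power in the cases examined.

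The issue is confined to the mechanism aim. The primary responder comparison is unaffected.

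**What to change.** 1. Add to Protocol 4.4 or 4.5, and to the SAP, a baseline-adjusted comparison of change in each gut marker at month 6 between the capsule arm and the TLC arm. Treat the other arms and months 1 and 3 as supportive.
2. Run the change-on-change association in all four arms, with terms for randomised arm and baseline values, and give a mediation-type estimate for capsule versus TLC. Report the arm-by-marker interaction as exploratory and do not require it for a mechanism claim. Present results without adjustment for BMI change, and with it only as a sensitivity analysis.
3. Describe the capsule-only correlations as exploratory association, and state that 165 to 180 tests are planned without multiplicity control.

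The cost is analysis text and programming, provided gut markers are measured at month 6 in every arm. The sponsor should confirm this. If only month 1 is available in all arms, make the contrast there. Even after these changes the link from marker to liver stays observational, because only the treatment is randomised.
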